### 3. VERSIONING

Version	Date	Author (First & Last name)	Pages or sections concerned	Nature(*)	Reason(s) for change (**)
1	14/06/2017	[name]	All	C	
2	15/06/2017	[name]	Section 2	M	Responsibility “Auditor” changed into “Reviewer”
2	15/06/2017	[name]	Section 14.1.4	M	Modification of patients subgroups with vascular or cardiac therapeutic procedures (deletion of onset restriction “<3months”)

(\*) C: Creation, M: Modification, A: Addition, D: Deletion

(\*\*) If the modifications are requested by external representatives (authorities), specify the organism name.

## 5. LIST OF ABBREVIATIONS AND DEFINITION OF TERMS

aPTT :	aPTT : Activated partial thromboplastin time
AE	Adverse Event
AF	Atrial Fibrillation
AP	Alkaline Phosphatase
ATC	Anatomical Therapeutic Chemical classification
BP	Blood Pressure
BSA	Body Surface Area
CNALV	Clinically Noteworthy Abnormal Laboratory Value
CRF	Case Report From
DBP	Diastolic Blood Pressure
DHA	Docosahexaenoic acid
eCRF	Electronic case report form
ECG	Electrocardiogram
ECV	Electrocardioversion
FDA	Food and Drug Administration
HLGT	High-Level Group Term
HLT	High-Level Term
HR	Heart Rate
ICH	International conference on harmonisation of technical requirements for registration of pharmaceuticals for human use
IDMC	Independent Data Monitoring Committee
INR	International normalized ratio
IVRS	Interactive voice response system
JNC	Joint National Committee
MedDRA	Medical Dictionary for Regulatory Activities
NYHA	New York Heart Association
PSC	Predefined Potentially Clinically Significant Change
PSCV	PSC leading to Clinically Significant Value
PT	Preferred Term
SAE	Serious Adverse Event
SAP	Statistical Analysis Plan
SAS	Statistical Analysis System
SBP	Systolic Blood Pressure
SD	Standard Deviation
SEM	Standard Error of Mean
SOC	System Organ Class
TB	Total Bilirubin
TCT	Thrombin clotting time
TE AE	Treatment Emergent Adverse Event
TTM	TransTelephonic ECG monitoring
WBC	White Blood Cells
WHODrug	World Health Organisation Drug

## 6. INTRODUCTION

This document describes the final statistical analysis of the study that will be performed after the lock of the clinical database and the randomisation code release on the total number of study patients.

This statistical analysis plan will be approved before the final Data Review Meeting, and finalised and signed prior to the final randomisation code release.

### **Study design**

This phase IIa trial is conducted as an international, multicentric, 24 weeks, double-blind, placebo-controlled, randomised, parallel group design, study on patients suffering from persistent AF and chronic heart failure.

### **Study objectives**

The primary objective of the study is to assess the efficacy of F373280 on the maintenance of sinus rhythm after direct ECV in patients with persistent AF and chronic heart failure.

The secondary objectives of the study are to assess:

- the efficacy of F373280 on the efficiency of direct ECV
- the effect of F373280 on echocardiographic parameters
- the safety and tolerability of F373280

### **Study treatment**

After a 1 to 4-week run-in period, patients are randomised into one of the following treatment groups: F373280 1g or placebo 1g for 24 weeks. The treatment starts 4 weeks before ECV and ECV is performed in patients with no spontaneous cardioversion and with INR levels stabilized as mentioned in the protocol. The follow-up is of 20 weeks after a successful ECV (at visit 3 – cardioversion visit) or after a spontaneous CV.

### **Primary efficacy criterion**

The primary criterion is the time to first Atrial Fibrillation recurrence or Atrial Flutter emergence defined by the time to first episode of Atrial Fibrillation or atrial flutter lasting for at least 10 minutes during the follow up of 20 weeks after visit 3 (ECV visit).

The cardiac monitoring is performed using:

- A 7-day continuous ECG ambulatory recording (Holter ECG) between visit 3 (ECV visit) and visit 4 (week 5) in patients cardioverted to sinus rhythm.
- A Trans Telephonic ECG Monitoring (TTEM):

\* before protocol amendment PA05: with a daily transmission from week 6 to week 8; then every two days from week 9 to week 24, and at anytime in case of AF symptoms

\* after protocol amendment PA05: with one transmission per week from the day of visit 4 (end of week 5) to visit 9 (week 24).

### **Sample size**

Assuming an AF recurrence rate of 85% under placebo and 65% under active group, i.e. a clinically relevant difference  $\Delta$  of 20%, a sample size of 64 assessable patients per group is

required, using a log-rank test of survival curves with a 80 % power and a 5 % two-sided significance level. According to the previous assumptions and assuming a rate of not assessable patients of 15%, a minimum of 76 patients have to be randomised per group. Due to low recruitment, it was decided to stop prematurely the study. 135 patients were finally randomised (instead of 152 initially planned).

### **Interim Safety reviews/IDMC recommendations**

Three IDMC were planned to provide independent safety review and trial guidance during the course of the ongoing trial (after the first 30 randomised patients, when the first 80 patients have terminated their study participation and then 130 patients). Due to the premature stop of the recruitment, only the first two meetings took place with IDMC recommendations to continue the study.

## STUDY FLOW-CHART (PROTOCOL VERSION 9 28/09/2016)

F373280 CA 201

Weeks	V1 W-4 to W-1	V2 D1	V3 W4 (28 -2D/+7 D)	V4 W5 (35 -2D/+7 D)	V6 W12 (84+/-7D)	V7 W16 (112+/-7D)	V9 W24 (168+/-7D)
Outpatient or Hospitalization (1)			X				
Informed consent	X						
Demographic characteristics	X						
Medico-surgical history	X						
Concomitant disease	X						
Concomitant treatment	X	X	X	X	X	X	X
Habits	X						
Global physical examination (body weight)	X	X	X		X	X	X
Echocardiography	X	X		X		X	
Eligibility criteria check	X	X					
Blood pressure, heart rate	X	X	X	X	X	X	X
12-Lead ECG Recording	X	X	X		X	X	X
INR					X		→ (2)
aPTT, TCT	X	X	X		X	X	X
Biochemistry	X						X
Haematology	X		X				X
Urinary pregnancy test			X				X
Red Blood Cell concentrations of DHA		X	X			X	X
Treatment number allocation			X			X	
IVRS/IWRS	X	X				X	
ECV (3)			X				
Drug administration							→
Adverse events recording		X	X	X	X	X	X
Holter ECG	↔ (4)		↔ (5)				
TTEM (6)							→

 Outpatient or hospitalization according to clinical practice of the centre (less or more than 24 hours) In case of VKA introduction: INR 2 to 3 times a week until stabilization, then weekly until the ECV, then every 4 weeks after ECV In patients with AF 24-hour Holter ECG 7-day Holter ECG TTEM: one transmission per week from the day of visit 4 (end of week 5) to visit 9 (week 24) and at any time in case of AF or atrial flutter symptoms.

TTEM once a week even in case of AF recurrence or atrial flutter emergence for at least 10 minutes.

**V5 et V8 were cancelled in the amendment PA05**

## 7. ANALYSIS SETS

The following analysis sets will be defined:

- **The Screened patients Set** which consists of all patients who have signed an informed consent,
- **The Randomised Patients Set** which consists of all patients who have signed an informed consent, and are assigned a treatment number,
- **The Safety Set** composed of all randomised patients having taken at least one dose of the study treatment. This set will be used to perform analyses of Safety.
- **The Full Analysis Set (FAS)** composed of all randomised patients having received at least one dose of the study treatment and with a successful cardioversion observed at visit 3. A successful cardioversion will be defined as either spontaneous cardioversion before V3 or successful ECV performed at V3 (early relapse within the observation period after ECV will be considered as non successful). This set will be used to perform analyses of Efficacy.
- **The Per Protocol Set (PP)** which is the subset of the Full Analysis Set composed of all FAS patients without any major protocol deviation or other source of bias for primary criteria analyses. This set will be used to perform the supportive analysis of the primary efficacy criterion.

Patients from Randomised Patients Set, Safety Set, Full Analysis Set or PP set will be analysed as treated (*ie* as treatment actually received at the randomisation). In case of error of treatment dispensation during the study period, the assignment of patient treatment group will be discussed during the data review meeting.

Randomised patients not treated will be analysed as randomised (*ie* as treatment allocated at the randomisation).

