## 13. DEMOGRAPHIC AND OTHER BASELINE CHARACTERISTICS

Before the first trial drug intake, medical and surgical history, demographic data (gender, age, weight, height and BSA) and disease characteristics (left atrial area in  $\text{cm}^2$ , left ventricular ejection fraction in %, duration of current AF up to selection visit (days), time from first

documented persistent AF up to selection visit, time from heart failure diagnosis up to selection visit, NYHA grade) will be described by treatment group on the Full Analysis Set.

These data, except disease characteristics and baseline efficacy criteria will also be described on the Safety set.

If more than 10.0% patients of the FAS are excluded from the Per Protocol Set, demographic data, disease characteristics and baseline efficacy criteria will be repeated on the PP Set.

The age in years will be calculated as the integer part of [(reference start date\* - date of birth)/365.25]. \*See appendix 1

For listings of individual data, the age presented for randomised and non treated patients will be (date of randomisation - date of birth) and the age for not randomised patients will be (date of informed consent signature dates - date of birth).

The BMI will be calculated as weight (kg) / [height (m)] rounded to 1 decimal place.

Time from first documented persistent AF and time from heart failure diagnosis up to selection visit will be calculated in months as (selection visit date – event date +1)/30.4, rounded to one decimal place.

Body weight, BSA, left atrial area and left ventricular ejection fraction at screening and inclusion visits will be described by treatment group only for baseline values (*i.e.* last values measured before the first application of study drug).

Concomitant diseases at selection, as well as medical and surgical history will be tabulated descriptively by treatment group using the MedDRA System Organ Classes and preferred terms on the Safety Set.

Concomitant treatments taken before first study drug intake date will be tabulated descriptively (number and percentage of patients) by treatment group on the Safety Set. They will be classified by therapeutic area according to the WHO-DRUG dictionary using the "anatomical therapeutic chemical" (ATC) classification, by WHO-DRUG ATC1 and ATC2 codes.

Concomitant treatments taken before first study drug intake date and linked to the study pathology will be also tabulated as above.

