Any factor which could bias the treatment effect estimate, like demographic data or any other baseline characteristics will be cautiously examined in order to determine whether the randomisation failed and affect the interpretation of the primary results. If this descriptive analysis provides any clues on potential imbalances, further statistical investigations will be carried out.

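### The primary comparison is conditional on sinus rhythm at V3, and no planned analysis shows whether it holds in all treated patients

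*SAP*

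**What the plan says.** - **Timing.** Section 6, Study treatment: "The treatment starts 4 weeks before ECV and ECV is performed in patients with no spontaneous cardioversion". Follow-up for recurrence runs 20 weeks from V3.
- **FAS.** Section 7 requires at least one dose and a successful cardioversion at V3, either spontaneous before V3 or by ECV at V3. It adds that "early relapse within the observation period after ECV will be considered as non successful". Section 18 records that the SAP itself clarified this definition.
- **Objective.** Section 6 lists among the secondary objectives "the efficacy of F373280 on the efficiency of direct ECV". Section 14.2.5.5 plans the between-arm comparison of cardioversion. Section 14.2 puts every secondary analysis on the FAS, and Appendix 5 labels the cardioversion table FAS.
- **Primary criterion.** It is analysed on the FAS (14, 14.1.1) and repeated on the PP Set, a subset of the FAS (14.1.2). The subgroups and Cox models of 14.1.4 are all within the FAS. Section 14.1.3 adds only predictive probability and conditional power.
- **Interpretation.** Section 8 allows a causal reading of the primary test alone.
- **Baseline.** Section 13 describes disease characteristics on the FAS, then says: "These data, except disease characteristics and baseline efficacy criteria will also be described on the Safety set". Appendix 5 has summary tables of them for FAS and PP only. Section 13 uses the baseline tables "in order to determine whether the randomisation failed and affect the interpretation of the primary results".
- **Exclusions.** Section 9 tabulates reasons for exclusion by arm on the Randomised Patients Set, and section 12 gives set sizes by arm.

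**The concern.** Entry to the efficacy population depends on an outcome measured after randomisation and after about 4 weeks of drug, and the SAP treats that outcome as something the drug may change. If the drug converts harder cases, the active FAS holds more patients prone to relapse and a maintenance benefit is understated. If it converts fewer, the active FAS is enriched for good prognosis and the benefit is overstated. The early-relapse rule adds to this: AF returning inside the observation period removes a patient, while an episode of at least 10 minutes soon afterwards is a primary event.

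Two planned checks are weaker than they look. Left atrial area, AF duration, LVEF and NYHA grade are summarised by arm only after selection at V3, so an imbalance in them is hard to attribute to randomisation or to selection. The cardioversion comparison on the FAS cannot compare overall success, because every FAS patient is a success by definition. Only the split between spontaneous and electrical conversion, the number of shocks and later cardioversions can differ.

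**Working it through.** **1. The plan's own figure.** Section 6, Sample size: "Assuming an AF recurrence rate of 85% under placebo and 65% under active group", "using a log-rank test of survival curves with a 80 % power and a 5 % two-sided significance level".
- HR = ln(1 − 0.65)/ln(1 − 0.85) = ln 0.35/ln 0.15 = 0.553.
- Freedman events = (1.960 + 0.842)² × [(1 + 0.553)/(1 − 0.553)]² = 94.9, so 95.
- Patients per group = 95/(0.85 + 0.65) = 63.3, so 64. This matches the plan.
- 64/(1 − 0.15) = 75.3, so 76 randomised per group. This also matches.

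The arithmetic is sound, but it concerns assessable patients only.

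**2. Missing input.** The SAP gives no conversion rate by arm. All conversion rates below are assumptions.

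**3. Harder cases entering the active FAS.** Assume 80% of placebo and 90% of active patients convert, with recurrence of 85% v 65% in the 80% who would convert on either arm. Active FAS recurrence is (80 × 0.65 + 10 × r)/90, where r is recurrence in the extra 10%.

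| r | Active FAS recurrence | Difference from 85% |
|---|---|---|
| 0.65 | 65.0% | 20.0 points |
| 0.85 | 67.2% | 17.8 points |
| 1.00 | 68.9% | 16.1 points |

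The last row is the worst case.

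**4. All-treated failure, with non-converters as failures.** Failure = 1 − P(convert) × P(no recurrence given conversion), taking 85% and 65% as the rates among converters.

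| Conversion, placebo/active | Placebo failure | Active failure | Difference |
|---|---|---|---|
| 85%/85% | 1 − 0.85 × 0.15 = 87.3% | 1 − 0.85 × 0.35 = 70.3% | 17.0 points |
| 75%/90% | 1 − 0.75 × 0.15 = 88.8% | 1 − 0.90 × 0.35 = 68.5% | 20.3 points |
| 90%/75% | 1 − 0.90 × 0.15 = 86.5% | 1 − 0.75 × 0.35 = 73.8% | 12.8 points |

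The FAS shows 20 points in all three. The fall to 17.0 with equal conversion is dilution, not bias.

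**5. Simulation of the FAS log-rank test.** 68 per arm (135/2 = 67.5), 1,500 runs. A standard normal severity lowers the log-odds of conversion (slope 1.5) and raises the log hazard of recurrence (slope 1.0). The baseline hazard gives 85% recurrence among placebo converters.

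| Drug effect on recurrence | Conversion, placebo/active | Severity affects recurrence | FAS rejection rate |
|---|---|---|---|
| None | 85%/85% | yes | 4.9% |
| None | 75%/90% | yes | 8.1% (mean z +0.49, against the drug) |
| None | 80%/95% | yes | 7.0% (mean z +0.50) |
| None | 75%/90% | no | 5.3% |
| HR 0.553 within severity level | 85%/85% | yes | 55% |
| HR 0.553 within severity level | 75%/90% | yes | 33% |

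Monte Carlo error near 5% is √(0.05 × 0.95/1500) = 0.6 points. Under no drug effect, swapping the arm labels turns the same shift in the drug's favour. A separate small simulation (1,500 per arm, error about ±0.05) gave a null FAS HR of about 1.0 to 1.2 when the drug raised conversion by 10 to 20 points, and about 0.91 to 0.92 when it lowered it by 10.

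**6. Limit of the all-treated test.** In the simulation at 75%/90% with severity unrelated to recurrence and no maintenance effect, it rejected in 17.7% of runs because it picks up the conversion effect.

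**The case against.** The strongest reply is that the objective is maintenance of sinus rhythm after ECV, and a patient never in sinus rhythm cannot have a recurrence. Conditioning on conversion is therefore part of the question. That stands, and is why the FAS should remain primary.

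Other safeguards also count. The tabulations in sections 9 and 12 would show unequal loss at V3, which is one precondition for bias. The Cox models in 14.1.4 examine left atrial area, AF duration, LVEF and NYHA grade, a partial check on measured prognosis. Demographics and medical history are described on the Safety Set too, and section 13 promises further work if imbalance appears. None of these shows what the primary result would be in all treated patients.

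The likely bias is also modest. With 135 × 0.85 ≈ 115 patients and 75% events (86), the standard error of log HR is about 2/√86 = 0.22. A null HR shifted to 1.10 is ln 1.10 = 0.095, or 0.44 of a standard error.

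A reader might infer that about 20 patients (15% of 135) will be lost to failed conversion. The Sample size paragraph does not say that a not-assessable patient is one who failed to convert, so that figure is indicative only.

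**Conclusion.** The point holds as a cheap improvement to the plan, not as a fault that invalidates the primary analysis. The FAS comparison is conditional on being in sinus rhythm at V3. Bias needs both different conversion by arm and a prognostic factor shared by conversion and recurrence. With both assumed, type I error was 7.0% to 8.1% and power fell from 55% to 33%; without the shared factor, type I error stayed near 5%. The SAP supplies evidence on neither condition, so size and direction are unknown.

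A reader might go further and conclude that the arms are no longer comparable, or that a positive FAS result should count only if an all-treated analysis agrees in direction. The SAP supports neither. Comparability is at risk, not shown to be lost. A requirement of agreement would let a conversion effect overrule a real maintenance effect.

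What is firmly established is that no analysis of the primary criterion leaves the FAS, that disease characteristics are summarised only after selection, and that overall cardioversion success cannot be compared on the FAS.

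**What to change.** 1. **Section 14.1.4.** Add one sensitivity analysis by arm on all randomised and treated patients, with time zero at V3. Count failed ECV, early relapse within the observation period, and AF at V3 with no ECV performed as events on day 1. Censor on day 1 patients who leave before V3 with no rhythm outcome, and count them as events in a second run.
2. **Section 13.** Describe disease characteristics by arm on the Randomised Patients Set as well, and use that table to assess whether randomisation failed.
3. **Section 14.2.5.5.** Compare cardioversion success on the Safety Set or the Randomised Patients Set.
4. **Sections 8 and 14.1.1.** Keep the FAS analysis primary, describe its result as conditional on conversion, and report it alongside the sensitivity analysis without making either depend on the other.

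The cost is SAP wording, one further set of Kaplan-Meier, log-rank and Cox outputs with its second run, one baseline table, and a change of set for the cardioversion table. The data are already collected, since V3 rhythm status is needed to define the FAS. Section 6 has the SAP signed before code release, so these changes count as prespecified only if made by then. The downside is that the added analysis mixes conversion with maintenance, and its events on day 1 may strain proportional hazards. It should stay a sensitivity analysis.

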## 8. INFERENTIAL PRINCIPLES

Only the test on the primary criterion, on which is based the sample size justification, may lead to a causal interpretation. All other statistical results are to be regarded as exploratory. Statistical tests will be two-sided and the significance level will be set to 5 %.

In order to obtain statistical modelling convergence and balance number of randomised patients, Poland (with only four randomised patients) will be grouped with the country that randomised the second lowest number of patients (Hungary). Categorical variable “Country” will be analysed with 4 levels for stratified statistical tests and statistical modeling: Italy, Spain, Czech Republic and Hungary.

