## 9. DEVIATIONS

A final data review meeting will be held, prior to database lock, in order to review protocol deviations. These will be classified as minor or major.

A protocol deviation will be considered as major when it is likely to bias significantly the treatment effect estimate based on the primary efficacy criterion.

Major protocol deviations and other sources of bias for primary criterion analyses, as well as additional reasons of exclusion from analysis sets will be identified using the list of pre-defined reasons for exclusion from analysis sets for the study described in a specific document “Predefined reasons for exclusion from analysis sets“ separately from the statistical analysis plan.

A listing of all deviations and a listing of additional reasons for exclusion from statistical analysis will be provided for all randomised patients, including the type (major/minor) as validated during the data review meeting. This listing should be provided prior to the database lock and the randomisation code release.

The number and percentage of patients with major protocol deviations will be tabulated by treatment group and type of major protocol deviations on the randomised patients set defined in section 7. The number and percentage of patients with minor protocol deviations will be also tabulated by treatment group and type of minor deviations on the randomised patients set.

The number and percentage of patients with reason of exclusion from analysis sets will be tabulated by treatment group and type of reason of exclusion on the randomised patients set.

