## 14. ANALYSIS OF EFFICACY

Unless otherwise specified, the efficacy analysis will be performed on the FAS. Baseline values will be the latest value measured before the first study drug intake.

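### Section 7 groups the FAS by treatment received and sets no rule for later dispensing errors, so any wrong-product patient would take the primary test away from the randomised comparison

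*SAP*

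**What the plan says.** SAP Section 7 (Analysis Sets) gives one rule for four sets: "Patients from Randomised Patients Set, Safety Set, Full Analysis Set or PP set will be analysed as treated". It explains the term as "as treatment actually received at the randomisation".

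Two provisions complete the rule:

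- Later errors: "In case of error of treatment dispensation during the study period, the assignment of patient treatment group will be discussed during the data review meeting".
- Patients who took no study drug: "Randomised patients not treated will be analysed as randomised". Here Section 7 refers to the allocated treatment.

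The rule reaches the primary test through two other sections. Section 14 states: "Unless otherwise specified, the efficacy analysis will be performed on the FAS". Section 8 states: "Only the test on the primary criterion, on which is based the sample size justification, may lead to a causal interpretation".

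On timing, Section 9 says: "A final data review meeting will be held, prior to database lock, in order to review protocol deviations". The deviation and exclusion listings are due before database lock and code release.

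**The concern.** The log-rank comparison can be read causally because chance decided who belongs to each arm. Grouping by product received keeps that property only while product received and arm allocated agree. Where they differ, Section 7 takes the product.

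Treatment received is the usual grouping for safety and can be defended for a per-protocol analysis. The difficulty lies with the FAS, and to a lesser degree with the Randomised Patients Set, whose disposition and deviation tables would also be grouped this way.

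The second weakness is the missing rule. For an error after the start of treatment, the SAP does not say whether the first kit, the longest exposure or the allocated arm decides the group. Two teams with the same data could form different primary comparison groups and both comply with the SAP.

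**Working it through.** **Step 1. Is 'as treated' only loose wording for 'as randomised'?** No. Section 7 uses treatment received for treated patients and treatment allocated for untreated ones, in adjoining paragraphs. The contrast is deliberate.

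**Step 2. Does any FAS patient fall under the as-randomised provision?** No. That provision covers untreated patients only, and FAS membership requires at least one dose. The two groups cannot overlap.

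**Step 3. Does another analysis supply the randomised comparison?** No. Section 14.1.2 repeats the primary analysis on the PP set, which has the same grouping rule. Section 14.1.3 adds predictive probability and conditional power. Section 14.1.4 adds subgroups, Cox models and ROC curves. None regroups patients by allocated arm, and Section 18 does not mention the rule.

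**Step 4. What does the rule settle?** For an error at the start, 'received at the randomisation' gives a definite answer. For an error later on, the text offers a discussion and no criterion. The meeting comes before lock and its listings before code release, so it should be blind to arm. The SAP does not say how a received arm is then established.

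**Step 5. What would as-randomised analysis of the FAS cost?** First, the plan's own sample size (Section 6), with 85% and 65% recurrence, 80% power and two-sided 5%:

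- HR = ln(0.35)/ln(0.15) = 0.553.
- Freedman events = (1.960 + 0.842)² × [(1 + 0.553)/(1 − 0.553)]² = 94.9, so 95.
- Patients per group = 95/0.75/2 = 63.3, so 64, as stated.
- Randomised per group = 64/0.85 = 75.3, so 76, as stated.

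These figures do not depend on the grouping rule.

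Next, power at the size reached. Section 6 reports 135 randomised. Assuming its 15% not-assessable rate holds, 135 × 0.85 = 114.75 are assessable and 114.75 × 0.75 = 86.1 have events. Power = Φ(√86.1 × (1 − HR)/(1 + HR) − 1.96).

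The SAP gives no error rate, so the table assumes a share m of each arm took the other product throughout. Recurrence under as-randomised grouping is then 0.85 − 0.20m and 0.65 + 0.20m.

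| m | Placebo | Active | HR | Power |
|---|---|---|---|---|
| 0 | 0.850 | 0.650 | 0.553 | 76% |
| 1% | 0.848 | 0.652 | 0.560 | 74% |
| 2% | 0.846 | 0.654 | 0.567 | 73% |
| 5% | 0.840 | 0.660 | 0.589 | 67% |
| 10% | 0.830 | 0.670 | 0.626 | 57% |

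The loss is small at 1% or 2% and material only at rates that would themselves be a serious supply failure.

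**The case against.** The strongest reply is that the problem is conditional and may be empty. The SAP reports no dispensing error, and without one the two groupings coincide. That stands, and it limits the severity.

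A second reply is that as-treated grouping need not distort the test here. In a double-blind trial with allocated treatment numbers, a wrong kit is a supply error. If errors are random and outcomes follow the product taken, simulation (57 per arm, exponential times, 85% v 65%, censoring at 20 weeks) gives type I error near 5%. With three wrong-kit placebo patients, power is about 78% as treated against 72% to 74% as randomised. This also stands, but it relies on errors being unrelated to prognosis, whereas the randomised grouping needs no such assumption. It also does not supply the missing rule for later errors.

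Three stronger readings are tempting, and the SAP does not support them:

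- **That the as-treated groups are self-selected.** Nothing suggests that a patient or investigator chooses the product.
- **That the meeting assigns arms knowing each patient's rhythm course.** Sections 7 and 9 do not say that rhythm data are presented, and the timing points to a meeting blind to arm.
- **That the rule forces unblinding before lock.** A blinded meeting could fix a rule by kit number and apply it after code release. The SAP does not say so, but does not exclude it.

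Finally, as-randomised labels would not make the FAS the full randomised comparison. The FAS is limited to patients with successful cardioversion at visit 3, after 4 weeks of treatment. That is correct and is a separate matter; it does not justify a second, avoidable departure.

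**Conclusion.** The point holds in conditional form. Section 7 groups the primary analysis by treatment received, leaves later dispensing errors without a criterion, and no planned analysis restores the randomised grouping. If one or more FAS patients received the wrong product, the only test that Section 8 allows to be read causally would no longer compare the arms as allocated.

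The size cannot be stated from the SAP. It is nil with no errors and unknown otherwise, because no count is given. A reader might infer that the primary result is biased; the SAP does not show this, either in direction or in amount. The power figures rest on the design recurrence rates, a 15% not-assessable rate and complete crossover of affected patients.

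This should be fixed before code release. It is a correction to the definition of the comparison groups and does not invalidate the trial.

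**What to change.** Revise the last two paragraphs of Section 7 as follows:

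1. Analyse the Randomised Patients Set and the FAS by the arm allocated at randomisation.
2. Keep treatment received for the Safety Set.
3. Replace the sentence on the data review meeting with a fixed rule, set before code release. One example for safety: group by the product in the first kit taken, identified by kit number and applied once the code is released.
4. Handle dispensing errors for the PP set through the separate document of predefined exclusion reasons named in Section 9. That document was not available here and may already cover them.
5. Record the change in Section 18, and note that the FAS remains conditional on successful cardioversion at visit 3.

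The cost is a few lines of text and one treatment variable per analysis set. The sample size is unchanged. The statistical downside is a slightly diluted effect estimate if errors occurred.
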